4.1.2.2 Endpoints

For fasting lipids (TG, TC, HDL-C, non-HDL-C, VLDL-C, and LDL-C), the Week 12 Endpoint is defined as an average of week 10 and week 12 measurements. For discontinued subjects, average of last non-missing two consecutive measurements up to week 12 is used as the week 12 Endpoint. If only a single measurement is available for a patient, it is used as the week 12 Endpoint.

For the other secondary efficacy parameters listed in section 3.2.2, if no measurement is available at Week 12, the last post-baseline single measurement up to Week 12 will be used if appropriate. Such cases will be presented as Week 12 (LOCF).

For any variables, last non-missing measurement up to Week 24/52 will be employed for Week 24/52(LOCF) evaluation if appropriate.

4.1.2.3 Percent change from baseline and change from baseline

Percent change from baseline to any Week t (protocol-planned visits or Endpoints as defined section 4.1.2.2) is defined as follows:

$$P_{Week t} = 100 \times (M_{Week t} - M_{baseline}) / M_{baseline}$$

where:

- $P_{Week t}$ is the percent change from baseline at Week t,
- $M_{Week t}$ is the measurement at Week t,
- $M_{baseline}$ is the measurement at baseline as defined in section 4.1.2.1.

Change from baseline to any Week t (or Endpoints) is defined as follows:

$$C_{Week t} = M_{Week t} - M_{baseline}$$
.

where $C_{Week t}$ is the change from baseline at Week t, and $M_{Week t}$ and $M_{baseline}$ are as defined above.

4.1.2.4 Study Day

Study Day is calculated from date of first dose of double-blind medication. The first dose date is defined as Day 1 and Study Day for each post-baseline assessment is attributed by Date of assessment – Date of first dose + 1. Study Day for assessment before first dose date will be calculated as Date of assessment – Date of first dose. Day 0 will not be used.

4.1.2.5 Visit windows and Unscheduled/Discontinuation visits

In principle, all the analysis will be performed based on nominal visit basis as reported in eCRF. Unscheduled/discontinuation visit will not be mapped to scheduled visit but will be used for Baseline and Endpoint/LOCF derivation and extreme values summary for laboratory values.

4.2 Analysis methods

4.2.1 Study population

4.2.1.1 Disposition

The disposition of subjects for the enrollment period and the double-blind treatment period (12 week, 24 weeks as well as 52 weeks) will be summarized.

The disposition summary of enrollment period will include all subjects enrolled (who signed informed consent).

The disposition summary of the treatment period will include all randomized subjects, and be presented by treatment group and total. This summary will include subjects completing and discontinuing the first 12-week, 24-week as well as 52 week treatment period with reasons for discontinuation.

4.2.1.2 Demographic and other baseline characteristics

Demographic and other baseline characteristics will be summarized by treatment group.

For continuous variables, descriptive statistics (n, mean, standard deviation, median, min, max) will be presented. For categorical variables number and proportion of patients in each category will be presented.

Demographic and baseline characteristics will include but not limited to age, gender, body weight, height, BMI, concurrent use of statin, baseline TG, baseline LDL-C and other baseline values of selected lipid parameters as well as some co-morbidities.

4.2.1.3 Medical/surgical histories and current medical conditions

The number (percent) of subjects with medical history findings and current medical conditions will be summarized by treatment group.

4.2.2 Efficacy

4.2.2.1 Analysis of primary efficacy variable

The primary efficacy variable is the percent change in TG from baseline to week 12 Endpoint. The primary efficacy analysis for the percent change in TG will be based on analysis of covariance (ANCOVA) model, with fixed categorical effects of treatment, statin usage, as well as continuous fixed covariate of baseline TG value. For comparisons of each AZD0585

dose vs. Placebo pair-wise comparison, variance estimated from each pair will be employed. Primary analysis will be carried out for FAS.

The model will provide least-squares (LS) mean estimates, standard errors and 2-sided 95% confidence intervals (CIs) for mean change at Week 12 Endpoint within and between treatments. Unadjusted two sided P-values will be calculated based on the model. Confirmatory hypothesis testing will be based on Hochberg procedure as described in section 4.1.1.1. If a (two-sided) p-value for either dose is less than 0.05/2 = 0.025, superiority of the corresponding AZD0585 dose to Placebo will be claimed. If both p-values (for 2g and 4g dose groups) are less than 0.05, then superiority of both AZD0585 doses to placebo will be claimed.

Sensitivity analysis of primary efficacy variable

To assess the robustness of the primary efficacy analysis, and to compare the results with previous studies, the sensitivity analyses on the primary efficacy variable will be carried out using the following approaches.

Per Protocol analysis

Primary analysis by the same ANCOVA model for percent change in TG from baseline to week 12 Endpoint will be repeated for Per-Protocol Set.

Analysis based on log transformation

Change from baseline in log-transformed TG values at Week 12 Endpoint will be analyzed by ANCOVA model with fixed categorical effects of treatment, statin usage, as well as continuous fixed covariate of log-transformed baseline TG value. LSmeans and 95%CIs for each treatment and treatment difference will be back-transformed and presented as mean percent change from baseline and as relative treatment difference to Placebo in percent change. Nominal p-values will also be reported from the models. The detail of transforming quantity from analysis in log scale to percent change is provided in the table below:

Table 2 Transformation of quantities from log-transformed analysis

Quantities	Derivation
Adjusted mean percent change from baseline	$100 \times [exp(Adjusted mean change from baseline in natural logarithm) - 1]$
Lower confidence limit for adjusted mean percent change from baseline	$100 \times [exp(lower confidence limit for adjusted mean change from baseline in natural logarithm) - 1]$
Upper confidence limit for adjusted mean percent change from baseline	$100 \times [exp(upper confidence limit for adjusted mean change from baseline in natural logarithm) – 1]$
Relative difference to Control in adjusted mean percent change from baseline.	$100 \times (exp(difference\ in\ adjusted\ mean\ change\ from\ baseline\ between\ AZD0585\ treatment\ arm\ and\ Control\ in\ natural\ logarithm) - 1)$

Quantities	Derivation
Lower confidence limit for relative difference to Control in adjusted mean percent change from baseline	100 × (exp(lower confidence limit for difference in adjusted mean change from baseline between AZD0585 treatment arm and Control in natural logarithm) – 1)
Upper confidence limit for relative difference to Control in adjusted mean percent change from baseline	100 × (exp(upper confidence limit for difference in adjusted mean change from baseline between AZD0585 treatment arm and Control in natural logarithm) – 1)

Nonparametric analysis

In order to address potential deviation from normality of percent change metric, treatment comparison on percent change of TG to Week 12 Endpoint will be conducted by two-sample Wilcoxon test. Treatment difference for location (median) shift will be presented with Hodges-Lehmann estimators and nonparametric 95%CIs.

Primary efficacy variable within subgroups

The primary efficacy variable of TG at Week 12 Endpoint will be descriptively summarized and analyzed similarly for the subgroups defined on the basis of the categorized variables listed in Table 3. Descriptive summary statistics would include, n, mean, standard deviation, minimum, 1st quartile, median, 3rd quartile, maximum.

Table 3 Subgroup analyses of primary efficacy variable

Group variable	Subgroups
Gender	Male, Female
Age	< 65 yrs >= 65 yrs
Body Mass Index	$< 25 \text{ kg/m}^2$ $>= 25 \text{ kg/m}^2$
Baseline triglyceride	< 300 mg/dL >= 300 mg/dL
Concurrent use of statin	Yes, No
Baseline LDL-C	< 140 mg/dL >= 140 mg/dL
Baseline HDL-C	< 40 mg/dL >= 40 mg/dL
Baseline non-HDL-C	< 170 mg/dL >= 170 mg/dL

Group variable	Subgroups
Baseline VLDL-C	< 60 mg/dL
	>= 60 mg/dL
Comorbidity – established CVD	Yes, No
Comorbidity – Hypertension	Yes, No
Comorbidity - Diabetes	Yes, No

4.2.2.2 Analysis of secondary efficacy variables

Fasting lipids (as defined in section 3.2.1)

The percent change from baseline of each fasting lipid parameter to the Week 12 Endpoint will be analyzed by ANCOVA model, with fixed categorical effects of treatment, statin usage, baseline TG strata (<300, >= 300 mg/dL) as well as continuous fixed covariate of corresponding baseline value. All the analyses will be carried out primarily for FAS and will be repeated for PPS.

The model will provide least-squares (LS) mean estimates, standard errors and 2-sided 95% confidence intervals for mean change at Week 12 Endpoint within and between treatments. Nominal two-sided p-values will also be displayed.

Other secondary efficacy parameters except for fasting lipids (as defined in section 3.2.2)

The percent change from baseline of each secondary efficacy parameter to Week 12 (LOCF) will be analyzed by ANCOVA model, with fixed categorical effects of treatment, statin usage, TG strata (<300, >= 300 mg/dL) as well as continuous fixed covariate of corresponding baseline value. All the analyses will be carried out for FAS only.

The model will provide least-squares (LS) mean estimates, standard errors and 2-sided 95% confidence intervals for mean percent change at Week 12 (LOCF) within and between treatments. Nominal two-sided p-values will also be displayed.

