8.5.2 Analysis of the secondary variable(s)

8.5.2.1 Efficacy variables

Percent change from baseline to the Week 12 Endpoint in TC, HDL-C, LDL-C, VLDL-C and non-HDL-C

Analyses will be carried out by ANCOVA model including percent change from baseline at Week 12 Endpoint as a response variable, treatment and baseline statin use and baseline TG strata (<300 , ≥ 300 mg/dL) as factors, and the corresponding baseline values as a covariate.

Percent change from baseline to Week 12 in Apo A-I, Apo A-II, Apo B, Apo B48, Apo C-II, Apo C-III, Apo E

Percent change from baseline to Week 12 in EPA, DHA, AA, EPA/AA ratio

Percent change from baseline to Week 12 in Small dense LDL, LDL-C/Apo B ratio

Percent change from baseline to Week 12 in Lp(a), RLP-C, PCSK9, hs-CRP

Analyses will be carried out by ANCOVA model including percent change from baseline at Week 12 as a response variable, treatment and baseline statin use and baseline TG strata (<300 , ≥ 300 mg/dL) as factors, and the corresponding baseline values as a covariate.

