1.3 Number of subjects

A common standard deviation of 24% is assumed for primary efficacy variable (Percent change from baseline to Week 12 Endpoint in serum TG). 150 patients in both of AZD0585 2 g and AZD0585 4 g and 75 patients in Placebo will ensure the power for detecting 12.5% difference of AZD0585 each dose vs. Placebo to be at least 92%, based on t-test with two-sided significance level of 0.05/2= 0.025, where approximate normality is assumed for the primary efficacy variable and significance level is conservatively adjusted for multiplicity for two comparisons by Hochberg procedure.

In the above calculation, it was assumed that a total of 375 patients are to be randomised to Placebo, AZD0585 2 g, AZD0585 4 g with ratio of 1:2:2 and that proportion of randomised patients not contributing primary analysis at Week 12 endpoint is negligible.

In addition, the above sample size is expected to be sufficient to provide long term safety data of more than 100 Japanese patients treated by AZD0585 2 g or by AZD0585 4 g for as long as

1 year assuming 10-15% drop out rate during 52-week treatment period, in accordance with Japan regulatory requirement.

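### The secondary ANCOVAs adjust for baseline TG only through the 300 mg/dL stratum; adding the continuous value is a small, optional gain in precision

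*SAP*

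**What the plan says.** SAP 4.2.2.2 gives one covariate set for both groups of secondary variables, the five fasting lipids and the 17 other markers. For the fasting lipids it reads "fixed categorical effects of treatment, statin usage, baseline TG strata (<300, >= 300 mg/dL) as well as continuous fixed covariate of corresponding baseline value". Protocol 8.5.2.1 specifies the same model for both groups: "Analyses will be carried out by ANCOVA model including percent change from baseline at Week 12 Endpoint as a response variable", with treatment, statin use and the TG stratum as factors and the corresponding baseline as covariate.

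The stratum uses the same 300 mg/dL cut as the randomisation, and statin use is the other stratification factor (Protocol 3.5, SAP 1.2).

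The primary model for percent change in TG (SAP 4.2.2.1) has treatment and statin use "as well as continuous fixed covariate of baseline TG value". There, TG is the endpoint's own baseline. SAP 4.1.2.1 derives it as an average of the week -4, -2 and 0 values, plus week -1 for patients who attended Visit 3a.

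SAP 4.1.1.1 treats everything other than the primary endpoint as descriptive, with no multiplicity adjustment. It offers 95% confidence intervals to convey precision.

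**The concern.** The plan treats baseline TG as relevant to the secondary markers: it stratifies on TG, puts the stratum in every secondary model and examines TG as a subgroup factor. Within that adjustment, a patient at 155 mg/dL and one at 295 mg/dL count as the same. The continuous value is already in the analysis dataset, so any association between TG and a marker's percent change within the two strata is left in the residual variance. Where such an association exists, the secondary confidence intervals are slightly wider than they need be. Precision of descriptive estimates is all that is at stake.

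**Working it through.** **The plan's own figure.** The only stated power belongs to the primary analysis. Inputs (SAP 1.3):

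- SD: "A common standard deviation of 24% is assumed for primary efficacy variable".
- Arm sizes: "150 patients in both of AZD0585 2 g and AZD0585 4 g and 75 patients in Placebo".
- Test: "based on t-test with two-sided significance level of 0.05/2= 0.025".
- Attrition: the "proportion of randomised patients not contributing primary analysis at Week 12 endpoint is negligible".
- Claim: these numbers "will ensure the power for detecting 12.5% difference of AZD0585 each dose vs. Placebo to be at least 92" per cent.

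Standard error = 24 × √(1/75 + 1/150) = 24 × 0.1414 = 3.394. Standardised difference = 12.5 / 3.394 = 3.683. The two-sided 0.025 critical value is 2.241, so power ≈ Φ(3.683 − 2.241) = 92.5%. The noncentral t with 223 degrees of freedom gives 92.2%. The figure reproduces, and nothing below touches it, because the primary model already has continuous TG.

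**Number of models affected.** 5 fasting lipids + 7 apolipoproteins + 4 fatty-acid measures + 2 LDL measures (small dense LDL, LDL-C/Apo B) + 4 others (Lp(a), RLP-C, PCSK9, hs-CRP) = 22.

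**How much TG information the stratum carries.** Let f be the squared correlation between TG and the indicator TG ≥ 300. The documents do not give this trial's TG distribution, so this step rests on an assumption: lognormal TG truncated to 150-499 mg/dL. For orientation, Protocol 1.1 reports a median of about 265 mg/dL in the overseas study of patients from 200 to below 500 mg/dL. Simulated values (median is the parameter before truncation):

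| Median (mg/dL) | log-SD | Share ≥ 300 | f |
|---|---|---|---|
| 200 | 0.25 | 5.9% | 0.40 |
| 200 | 0.35 | 15.1% | 0.61 |
| 230 | 0.25 | 15.0% | 0.55 |
| 230 | 0.35 | 24.1% | 0.66 |
| 265 | 0.25 | 31.0% | 0.65 |
| 265 | 0.35 | 35.8% | 0.69 |
| 300 | 0.25 | 49.1% | 0.65 |
| 300 | 0.35 | 47.3% | 0.69 |

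So f runs from about 0.40 to 0.69.

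**Effect on interval width.** Let R² be the partial R² of continuous TG for a marker's percent change, given own baseline and statin use. If the association is linear and similar across arms, and f also applies after those covariates, then:

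width with continuous TG / width with stratum only = √[(1 − R²) / (1 − f·R²)]

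| Partial R² | f = 0.40 | f = 0.69 | Narrowing |
|---|---|---|---|
| 1% | √(0.990/0.9960) = 0.9970 | √(0.990/0.9931) = 0.9984 | 0.2-0.3% |
| 5% | √(0.950/0.9800) = 0.9846 | √(0.950/0.9655) = 0.9919 | 0.8-1.5%, about 1% |
| 10% | √(0.900/0.9600) = 0.9682 | √(0.900/0.9310) = 0.9832 | 1.7-3.2%, about 2-3% |

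**Cost of the extra term.** With 375 patients the present model has 6 parameters (intercept, two for treatment, statin use, stratum, own baseline), leaving 369 residual degrees of freedom. One more covariate inflates the standard error by roughly 1/(2 × 369) = 0.14%. At a partial R² of 1% that cancels about half or more of the gain. From about 5% upwards it is immaterial.

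**The case against.** The strongest reply is that the plan is coherent as it stands, and most of that reply is right.

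- A reader comparing the two models might infer that the secondary analyses downgrade a covariate which the primary model uses in full. They do not. Both follow one rule: the endpoint's own baseline enters as a continuous covariate. In the primary model that baseline happens to be TG; in the secondary models it is the marker's, kept in full. The TG stratum is an additional term.
- Adjusting for a stratification factor at the cut used in randomisation is standard practice, and the term should stay.
- A reader might also infer bias from chance TG imbalance within strata. Randomisation makes that imbalance zero on average, and the confidence interval already reflects it.
- The analyses are descriptive, carry no alpha and have no stated power. Protocol and SAP agree on the model.
- The relevant R² is partial, and the outcome is a percent change. Prognostic value of TG for marker levels is not enough, and the documents give no figure for any marker.
- Three or more averaged TG values cannot be assumed for every patient, because the full analysis set requires only some baseline measurement (SAP 2.1).

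What remains is narrow. Precision is the stated use of the secondary intervals, and a collected covariate that might improve it is used only in two-level form.

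**Conclusion.** The point holds as a minor, optional improvement, not as a defect. All 22 secondary models adjust for TG only through the stratum. Adding the continuous value would narrow the descriptive 95% intervals by about 0.2-0.3%, 1% or 2-3% at a partial R² of 1%, 5% or 10%.

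These sizes rest on an assumed lognormal TG distribution and on partial R² values that the documents do not supply. A gain of 5-9% would need a partial correlation near 0.5 (R² of 25%), for which the documents offer no support.

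Nor do the documents support expecting the same gain for all 22 variables. It should be near zero for VLDL-C and RLP-C, whose own baselines can be expected to track TG, and for any marker whose percent change is unrelated to TG. No confirmatory conclusion, type I error rate or stated power is affected.

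**What to change.** In SAP 4.2.2.2, add baseline TG (or log TG) as a continuous covariate to the secondary ANCOVAs, using the averaged baseline already defined in SAP 4.1.2.1. Keep the TG stratum, statin use and the marker's own baseline. Record the departure from Protocol 8.5.2.1 in SAP section 6.

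The cost is one model term, one degree of freedom and one entry in section 6; no new data are needed. The timing matters: the secondary Week 12 analyses are run at the interim, when the sponsor is unblinded (SAP section 5), so the change must be written in before then to remain prespecified. If the sponsor prefers the present model, one sentence saying that the randomisation stratum is the intended TG adjustment would close the point.

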4.2.2.3 Analysis of exploratory efficacy variables

The time course of continuous efficacy variables will be presented using descriptive summary statistics by treatment and visit. For Week 12 Endpoint and Week 52 Endpoint, absolute change from baseline and percent change from baseline will also be presented. Descriptive summary statistics would include, n, mean, standard deviation, minimum, 1st quartile, median, 3rd quartile, maximum.

Descriptive summaries for selected secondary variables (including fasting lipids) will also be provided if deemed necessary based on the subgroup defined in Table 3.

4.2.3 Safety

For all safety evaluation, safety set will be used. In general, safety will be evaluated for the first 12-week treatment period as well as for 24-week or 52-week treatment period respectively at interim data base lock as well final data base lock.

4.2.3.1 Extent of exposure

Study medication

The extent of exposure to study medication is defined as last dose data - first dose date + 1.

The number and percent of subjects with an extent of exposure within pre-specified day ranges will be presented by treatment group. The categorization will be >=1 day, >= 4 weeks, >= 8 weeks, >= 12 weeks, >= 24 weeks, >= 36 weeks, >= 48 weeks and >= 52 weeks. The mean, standard deviation (SD), median and range of the number of days of exposure will also be presented.

Concomitant statin at baseline

Concurrent use of statin at baseline will be identified as those used at randomization day. Number of patients treated by statin at baseline will be summarized by treatment group, broken down by statin generic name.

General prior and concomitant medications

Prior medication will be defined as any medication taken before first dose of study drug. Concomitant medication will be defined as any medication taken on or after first dose of study medications. Medication which started before first dose of study drug and continued during study treatment will be counted in both prior medication and concomitant medication.

Prior and concomitant medications will be summarized using the Safety Set by drug class and (generic) drug name. A summary table by drug class and generic drug name will be generated for each of the following:

- all prior medication (excluding lipid lowering medication)
- all concomitant medication (excluding lipid lowering medication) taken during the first 12-week treatment period
- all concomitant medication (excluding lipid lowering medications) taken during the first 24-week treatment period
- all concomitant medication (excluding lipid lowering medications) taken during the whole treatment period (up to 52 weeks)
- prior lipid lowering medication
- concomitant lipid lowering medication during first 12-week treatment period

- concomitant lipid lowering medication during first 24-week treatment period
- concomitant lipid lowering medication during the whole treatment period (up to 52 weeks)

The WHO dictionary is used to code the non-study medication.

4.2.3.2 Adverse events

Treatment-emergent adverse events (TEAEs, i.e. adverse events with onset on or after first dose of study drug) will be summarized for safety evaluation. Adverse events occurring before start of study drug will only be listed.

Adverse events (AEs) will be classified by Primary System Organ Class (SOC) and Preferred Term (PT) according to the Medical Dictionary for Regulatory Activities (MedDRA). Summaries of AEs will use the version of MedDRA that is current at the time of database lock

All adverse events

All AEs with onset during the first 12-week (+2 days) treatment period, 24-week (+7 days) treatment period and with onset during the whole study treatment period will be summarized. The following items will be summarized by system organ class, preferred term and treatment group.

- Any AEs
- Deaths
- Serious AEs (SAEs)
- AEs leading to study drug discontinuation (DAEs)
- AEs by maximum intensity
- AEs related to study drug

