3.9.1 Procedures for discontinuation of a subject from investigational product

At any time, subjects are free to discontinue investigational product or withdraw from the study (i.e., investigational product and assessments – see Section 3.10), without prejudice to further treatment. A subject that decides to discontinue investigational product will always be asked about the reason(s) and the presence of any AEs. If possible, they will be seen and assessed by an Investigator(s). AEs will be followed up (see Section 6); diary cards and all study drugs should be returned by the subject. If the patient discontinues the study during the treatment period (by Visit 18), the test and evaluations planned at Visit 18 should be performed unless the patient refuses the procedure.

If a subject is withdrawn from study, see Section 3.10.

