3.10 Criteria for withdrawal

Subjects may be withdrawn from the study in the following situations:

- Subject decision. The subject is at any time free to withdraw from study
- AE
- Severe non-compliance with the study protocol, as judged by the investigator(s) or AstraZeneca
- Incorrect enrolment of the patient
- Patient falls into exclusion criteria, e.g., pregnancy
- Death
- Patient lost to follow up

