Question Adherence to TLC diet		X			X	X	X	X	X	X	X	X	X	X	X	X	X	X	X		X	
Dispense Investigational Product					X	X	X		X	X	X	X	X	X	X	X	X	X	X			
Assess Investigational Product Compliance						X	X		X	X	X	X	X	X	X	X	X	X	X		X	
AEs/SAEs ^f	←																				→	
Concomitant and other treatments	←																					→

^a If a patient withdraws before completion of 52 weeks of treatment, withdrawal visit should be carried out to evaluate the patient's safety.

^b If the investigators decide that an additional test is appropriate, Visit 3a is allowed. See section 3.1, 2nd inclusion criterion for details.

^c All examinations to be completed before randomisation.

^d Brief physical findings consisting of an evaluation of general appearance, respiratory, cardiovascular, abdomen, skin, head and neck (including ears, eyes, nose and throat), lymph nodes, thyroid, musculo-skeletal (including spine and extremities) and neurological systems.

^e Clinical assessments: Subjects will be questioned regarding the occurrence and nature of any symptoms and signs. Weight will be measured at each time; however, height will be measured only at Visit 1 to determine the body mass index (BMI).

^f SAEs will be recorded from the time of informed consent (Visit 1), and non-serious AEs will be collected from time of randomisation (Visit 4).

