6.3 Recording of adverse events

6.3.1 Time period for collection of adverse events

AEs will be collected from randomisation (Visit 4) until Visit 18 (or Visit 19).

SAEs will be recorded from the time of informed consent (Visit 1) until Visit 18 (or Visit 19).

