6.3.2 Follow-up of unresolved adverse events

Any AEs that are unresolved at the subject's last visit in the study are followed up by the investigator for as long as medically indicated, but without further recording in the eCRF. AstraZeneca retains the right to request additional information for any subject with ongoing AE(s)/SAE(s) at the end of the study, if judged necessary.

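### The 52-week adverse event summaries take no account of time at risk, so unequal dropout would bias the comparison between arms, slightly at the planned dropout rate

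*SAP*

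**What the plan says.** The second primary objective (Protocol 2.1, SAP 1.1.1) is safety up to 52 weeks. Protocol 1.2 expects the double-blind placebo comparison to give some view of whether AEs depend on dose.

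**Recording.** Protocol 6.3.1: "AEs will be collected from randomisation (Visit 4) until Visit 18 (or Visit 19"). The same end point applies to serious events: "SAEs will be recorded from the time of informed consent (Visit 1) until Visit 18 (or Visit 19"). Visit 19 is the withdrawal visit; the footnote to the study plan table says "If a patient withdraws before completion of 52 weeks of treatment, withdrawal visit should be carried out to evaluate the patient's safety". Under Protocol 6.3.2, events unresolved at the last visit are followed by the investigator "but without further recording in the eCRF".

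**Analysis.** SAP 4.2.3.2 summarises "All AEs with onset during the first 12-week (+2 days) treatment period, 24-week (+7 days) treatment period", and then the whole treatment period. Each window contains the one before it. The summaries are any AE, deaths, SAEs, AEs leading to study drug discontinuation (DAEs), maximum intensity and related AEs. No person-time rate, time-to-event summary or consecutive-period table is named.

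**Exposure and dropout.** SAP 4.2.3.1 tabulates days of exposure by arm, with categories up to 52 weeks, and SAP 4.2.1.1 gives disposition at 12, 24 and 52 weeks. Neither is linked to AE incidence. SAP 1.3 plans the sample size "assuming 10-15% drop out rate during 52-week treatment period", as one figure for the whole trial.

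**The concern.** In a percentage of patients with an event, someone observed for 6 weeks counts in the denominator exactly as someone observed for 52 weeks. Events after that person leaves are not seen. If one arm loses more patients, or loses them sooner, its whole-period percentage falls for a reason unrelated to the drug. Were that an active arm, the comparison with placebo and the reading across doses would both look too favourable.

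The nested windows add a second, lesser difficulty. An event type that begins after Week 24 appears only inside the whole-period total, mixed with earlier onsets. The AE tables do not say how many patients were still observed when the late period began. Background treatment also changes: Protocol 3.8 restricts lipid-lowering drugs up to Visit 8 (Week 12) and then allows them, except omega-3. Early and late events therefore arise under different conditions.

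The safety comparison is descriptive, so these tables are themselves the primary safety result.

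**Working it through.** **The plan's own figure.** SAP 1.3 expects more than 100 patients treated for one year. With 150 per active arm, 150 × 0.90 = 135 and 150 × 0.85 = 127.5. The figure reproduces for each active arm and holds up to 1 − 100/150 = 33% dropout. Long-term exposure is adequate; the issue is how AEs are summarised.

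**Inputs.** Arms of 150, 150 and 75, and 10–15% dropout overall (SAP 1.3). The documents give no AE rates and no dropout by arm, so those below are assumptions. True risk is equal in the arms compared unless stated.

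**Check A: dropout at a fixed week.** Assume a true 52-week risk of 20% and a constant hazard h = −ln(0.8) = 0.223 per 52 weeks. A fraction f leaves at week w. Crude risk = (1 − f) × 0.20 + f × (1 − exp(−h·w/52)).

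| Active | Placebo | Crude risks | Apparent RR | Overall dropout |
|---|---|---|---|---|
| 15% at Week 26 | 10% at Week 26 | 18.6% vs 19.1% | 0.975 | (45 + 7.5)/375 = 14% |
| 15% at Week 6 | 5% at Week 26 | 17.4% vs 19.5% | 0.89 | (45 + 3.75)/375 = 13% |
| 20% at Week 8 | 10% at Week 26 | 16.7% vs 19.1% | 0.875 | (60 + 7.5)/375 = 18% |

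The third row lies outside the planned overall range. The second lies inside it, but needs three times the dropout on active and all of it at Week 6.

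**Check B: dropout spread evenly.** Assume a true risk R = 10%, with onset possible from week t0, so λ = −ln(0.9)/(52 − t0). Dropout d by Week 52 gives μ = −ln(1 − d)/52. Crude risk = exp(−μ·t0) × λ/(λ + μ) × (1 − exp(−(λ + μ)(52 − t0))).

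| Onset | 10% dropout | 15% | 25% | RR, 15 vs 10 | RR, 25 vs 10 |
|---|---|---|---|---|---|
| Throughout | 9.50% | 9.24% | 8.71% | 0.973 | 0.917 |
| After Week 24 | 9.26% | 8.89% | 8.12% | 0.960 | 0.877 |
| After Week 36 | 9.15% | 8.72% | 7.85% | 0.953 | 0.858 |

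At 15% against 10% the spurious gap is 0.26 to 0.43 points. The standard error of a 150 vs 75 difference at 10% is √(0.1 × 0.9 × (1/150 + 1/75)) = 4.2 points. With a true ratio of 1.5 (15% vs 10%, onset after Week 24) and 10% placebo dropout, the apparent ratio is 1.44 at 15% active dropout, 1.32 at 25% and 1.25 at 30%.

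**Check C: does a rate per time at risk help?** For onset throughout, mean time to first event or dropout is 46.9 weeks at 10% dropout and 45.6 at 15%. The rates are 9.50/(46.887/52) = 10.5 and 9.243/(45.618/52) = 10.5 per 100 patient-years (taking 52 weeks as a year), so the gap disappears. For onset only after Week 24, they are 9.265/(48.047/52) = 10.03 and 8.890/(46.747/52) = 9.89. That ratio is 0.986 against 0.960 crude: most of the gap goes, not all of it.

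**Check D: nested windows.** Assume a 24-week risk of 10% in both arms, no dropout, and the hazard doubled after Week 24 in one arm. Whole-period risks are 29.6% and 20.4%, ratio 1.45. Subtracting the 24-week figure gives 19.6/10.4 = 1.88, which equals the true late-window risk ratio. With a 24-week risk of 50%, the whole-period ratio is only 1.16 (90.1% vs 77.7%). Subtraction recovers the late ratio here because the numbers at risk at Week 24 are proportionally equal; unequal dropout removes that.

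**The case against.** The best defence is that the bias is trivial under plausible dropout and that the plan already supplies most of what is needed. Much of this stands. A gap of 0.3 to 0.4 points is far below the 4.2-point standard error. Safety is descriptive, with no test (SAP 4.1.1.2). Arm size times mean exposure gives approximate person-time, and the exposure categories at 12, 24, 36, 48 and 52 weeks, with disposition, approximate the patients still at risk. The amendment history shows that the sponsor took out an AE-by-period table as not relevant to the report. SAP 4.2.3.2 says only that AEs are summarised, so reading this as crude percentages is an inference. What the defence does not supply is a planned rate: a reader must assemble one, from drug exposure rather than time to first event.

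A reader might go further in four ways that the documents do not support.

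- *Recording stops when treatment stops.* Protocol 3.9.1 separates the two events: "At any time, subjects are free to discontinue investigational product or withdraw from the study". Recording ends at Visit 18 or 19. The patient off drug but still in the study is left undefined; no rule ends recording at the last dose.
- *Events that cause withdrawal are lost.* Protocol 3.10 permits withdrawal for AEs and where "Patient falls into exclusion criteria, e.g., pregnancy" applies. But the AE that leads to withdrawal has already occurred, is counted, and appears among the DAEs. Only later events go unseen.
- *Late-onset risk cannot be shown.* Subtracting windows gives first onsets after Week 24 (Check D), and laboratory values, vital signs and ECG are summarised by visit.
- *SAE outcomes are lost.* Protocol 6.4 requires sites to report follow-up information on SAEs, Protocol 9.4 reconciles SAEs with the safety database, and Protocol 6.3.2 lets the sponsor ask for more on ongoing events.

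**Conclusion.** The point holds as a cheap improvement to the analysis, not as a flaw that threatens the trial. The primary safety summaries ignore time at risk, and under unequal dropout the whole-period percentages favour the arm that loses more patients or loses them sooner. For equal true risk at 15% against 10% dropout, the apparent ratio is about 0.97 (0.95 to 0.96 for late-onset events). It reaches 0.875 to 0.89 in Check A only under larger or earlier imbalance, and 0.86 to 0.92 in Check B at 25% against 10%. Late-onset events are shown poorly rather than not at all.

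The sizes rest on assumed AE risks, constant hazards from the start of onset, dropout independent of the event, and assumed dropout by arm. Because dropout by arm cannot be known in advance, the rates should be specified beforehand rather than added once an imbalance is seen.

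**What to change.** In SAP 4.2.3.2, for the whole-period summaries of any AE, SAEs, DAEs and related AEs, add exposure-adjusted incidence rates by arm beside the percentages. Define the rate as patients with a first event per 100 patient-years at risk, with time running from first dose to the first event or the end of AE observation. State what ends observation: Visit 18, Visit 19, or the last contact if neither took place.

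Optionally, show first-onset AEs for >12–24 and >24–52 weeks, with patients still under observation as denominators. This is the weaker part, given that a by-period table was judged not relevant, but it addresses what a whole-period rate leaves behind for late-onset events (Check C).

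The cost is a few descriptive tables from dates already collected, with no new visits or data entry. The rates assume a roughly constant hazard and dropout independent of later events, so they do not cure event-driven dropout; a footnote should say so.
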